## Number of predictors for mediations analysis

Based on our sample size of n=130 and the use of multiple regression models, power of >80% and alpha level of 5% (t = 1.658, Df = 109), we calculated the potential number of predictors as 16 based on Fritz & MacKinnon sample size recommendations for mediation analysis (G\*power 3.1.9.7, Düsseldorf University, Germany). In our current model, we have included 15 predictors (8 mediators and 7 potential covariates/moderators).

Variables	Measurement	Justification
Potential moderators/c	ovariates	
Growth velocity w0	Offset from predicted age at peak height velocity in years, calculated from clinically measured anthropometrics: sitting height, bodyweight, total stature, biological age.  Participants will be categorized into pre- (<-1.0 years offset), circa- (-1.0 to +0.5 years offset), and post-PHV (>+0.5 years offset), corrected for timing of the primary endpoint, resulting in a 5 month subtraction.	Overuse knee injuries, as well as injuries to the growth plate, in sports active adolescents are higher during peak height velocity and the year leading up to this point,  which is thought to be primarily due to vulnerable growth-related conditions, such as Osgood-Schlatter.  This has been supported by data showing higher growth velocity for Osgood-Schlatter patients than controls. 
Growth timing w0	Based on algorithms for calculating anticipated age of peak height velocity which incorporates data on parents adult stature, we will classify participants as early maturers, average maturers, and late maturers (girls: <10.94, 10.94-12.94, and >12.94 years, respectively; boys: <12.64, 12.64-14.64, and >14.64 years, respectively). 	Reaching skeletal maturity either late or on average is a risk factor for developing Osgood-Schlatter compared to early maturation. 
Fear of movement w13	Fear of movement will be captured by participants filling in the 17 items Tampa Scale of Kinesiophobia, each item scored on a 4-point likert scale with a score ranging from 0 to 68. 	Avoidance behavior might be related to a too apprehensive approach to gradual exposure and exercise therapy resulting in the patient not achieving a higher degree of participation in sports and physical activity. Osgood-Schlatter patients exhibits a high degree of kinesiophobia. 

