#### Step 3: run regression model

[figure not shown]
```
#runs linear regression model with `koos_spor't as the dependent outcome variable
#and `group' as the independent predictor variable. The model is named lm_koos_sp
#`timing' of maturation is included as a covariate.
```

```
lm_koos_sp <- lm(koos_sport~group + timing, data=fu_data)</pre>
```

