#### Step 6: evaluate model output from console

```
Residuals:
  Min 1Q Median 3Q Max
-4504.4 -2863.1 485.1 2421.4 4720.6
Coefficients:
        Estimate Std. Error t value Pr(>|t|)
(Intercept) 4541.2 2215.4 2.050 0.0498 *
         1050.6
                  1145.6 0.917 0.3670
group
         -1056.5
                   776.5 -1.360 0.1845
timing
___
Signif. codes: 0 `***' 0.001 `**' 0.01 `*' 0.05 `.' 0.1 ` ' 1
Residual standard error: 3105 on 28 degrees of freedom
 (2 observations deleted due to missingness)
Multiple R-squared: 0.07503, Adjusted R-squared: 0.008959
F-statistic: 1.136 on 2 and 28 DF, p-value: 0.3356
Linear regression of KOOS-child sport/rec
Dependent variable:
               _____
                      koos_sport
_____
                       1,050.577
group
                      (1, 145.632)
                      t = 0.917
                       p = 0.367
timing
                       -1,056.458
                       (776.549)
                       t = -1.360
                       p = 0.185
                      4,541.163**
Constant
                       (2, 215.364)
                       t = 2.050
                       p = 0.050
-----
Observations
                          31
                        0.075
R2
Adjusted R2
                        0.009
Residual Std. Error 3,104.971 (df = 28)
```

F Statistic	1.136 (df = 2; 28) (p = 0.336)
Note:	*p<0.1; **p<0.05; ***p<0.01

We expect only to modify these procedures if more suitable methods, packages, or software is developed and will describe and justify these potential deviations from the pre-specified strategy in the final report. Intention-to-treat analyses, that is, analysis according to group allocation, will be performed as the standard analysis strategy unless otherwise denoted, to 1) investigate the relative effectiveness of being offered the experimental intervention over usual care, and 2) to maintain the balance of known and unknown confounders from randomization.

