We will employ a similar analysis strategy for other numerical outcome variables. For non-numeric variables, differences between groups will be analyzed by logistic regression models, and non-normally distributed residuals for ratio-interval scale outcomes will be compared by non parametric boot strap tests. To supply detailed trajectories and inferences of treatment response over time, we will fit mixed-effects models for the imaging outcomes (months 0, 3, 5, 8); time-to-return to sport, weekly hours of sports participation, pain-flares, and sensor-based physical activity (weeks 0 to 22); clinical outcomes (months 0, 1, 3, 5, 8); and remaining patient-reported outcomes (months 0, 1, 3, 5, 8, 12, 24, 48).

Mean and SD values will be reported if data appear approximately normally distributed. If data are nonnormally distributed, they will be presented as median and interquartile range (IQR). We will report 95% confidence intervals, exact p-values to the third decimal, and discussions of minimal detectable change (MDC) and minimal important change (MIC) when relevant/possible. Frequency data will be reported as "No. (%)".

Our standard option for all variables, is to be analyzed with the highest resolution possible, meaning no collapsing or dichotomization to retain as much information as possible in the dataset. However, some assessor-dependent scales, such as ultrasound scoring of the (non-normal maturation-related) fragmentation quality of the tibial tubercle bone, contains the potential values "none" (1), "unclear", (2), "little", or "apparent/extensive" (4). The same applies to some other ultrasound measures and clinical examination findings. Depending on the distribution of responses into these categories, we might choose to exclude data from the "unclear" category or collapse the "little" and "apparent/extensive" categories if we estimate the number of responses to be too low to make meaningful inferences.

Once the primary data have been analyzed, we will also compute and report the RCT-Fragility Index (how

many patients would need to change from success to non-success to render the potential experimental effect non-significant or equal) based on the PASS outcome for easier clinical interpretation of the robustness of results.

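### Growth timing, a computed age in years, is cut into three classes in Table 12 without a stated reason and against the plan's default of no collapsing; if moderation is graded, this loses information

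*Combined protocol and SAP*

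**What the plan says.** Table 12 lists growth timing among the potential moderators and covariates. It is an anticipated age at peak height velocity obtained from an algorithm, after which "we will classify participants as early maturers, average maturers, and late maturers". The cut-points are sex-specific: "girls: <10.94, 10.94-12.94, and >12.94 years, respectively; boys: <12.64, 12.64-14.64, and >14.64 years, respectively". The justification is "Reaching skeletal maturity either late or on average is a risk factor for developing Osgood-Schlatter compared to early maturation".

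The section on statistical methods for primary and secondary outcomes, in the text after the code example, sets a general default: "Our standard option for all variables, is to be analyzed with the highest resolution possible, meaning no collapsing or dichotomization". The exception follows directly: "However, some assessor-dependent scales, such as ultrasound scoring". It extends to some other ultrasound measures and clinical examination findings, and applies when a category holds too few responses.

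Growth timing also appears in the example code as a covariate, without an interaction: "lm_koos_sp <- lm(koos_sport~group + timing, data=fu_data". The row above it in Table 12, growth velocity offset, is also computed in years and is cut into pre-, circa- and post-peak classes at -1.0 and +0.5 years.

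**The concern.** Growth timing is calculated from measurements; nobody rates it by eye. It is therefore outside the exception, and Table 12 does not say why the default is set aside. The justification concerns the risk of developing the condition, not response to treatment.

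The average class is two years wide. A participant 0.9 years early and one 0.9 years late are treated as identical, while two who differ by days across a cut are treated as different. If the treatment effect changes gradually with growth timing, information is thrown away.

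Finding out who benefits more or less is a stated secondary aim, and recruitment is complete at 130, so a larger sample cannot make up the loss. The Table 12 variables may also enter the primary model as covariates, and they act as moderators in the mediation model.

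**Working it through.** **The plan's own figure.** A two-sample one-sided t-test with difference 9, SD 16, alpha 5% and power 90% gives 54.8 per group, as stated. Then 110 / 0.85 = 129.4, rounded up to 130. The documents state no power, interaction size, sidedness or coding for any moderation test.

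**Inputs from the documents.** n = 130 in two equal groups; outcome SD 16, used here as the residual SD; cuts one year either side of 11.94 (girls: 10.94 + 1.00) and 13.64 (boys: 12.64 + 1.00).

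**Assumed inputs.** Predicted age at peak height velocity is normal around the sex-specific midpoint with an SD of 0.5 to 1.0 years; moderation is linear, b KOOS-child points of treatment effect per SD; the test is two-sided at 5%.

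**Information kept.** With a = 1/SD and p = 1 - Φ(a), the average class holds 1 - 2p. A score of -1, 0, 1 has variance 2p and covariance 2φ(a) with standardised timing, so it keeps R² = 2φ(a)²/p of the variance. At SD 1.0: 2 × 0.242² / 0.1587 = 0.74. At SD 0.5: 2 × 0.054² / 0.0228 = 0.26.

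**Power for b = 8, n = 130.** The non-centrality for the continuous term is n·b²/(4 × 16²) = 130 × 64 / 1024 = 8.125, which gives 81% power. For the score it is 8.125·R² / (1 + 0.0625(1 - R²)), where 0.0625 = 64/1024. That is 5.90 at SD 1.0 (67% power) and 1.99 at SD 0.5 (29%), a loss of about 13 to 52 points. Simulation, 4000 runs per cell, gives:

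| SD (years) | In average class | Variance kept by score | Continuous | Class score | Three-class factor |
|---|---|---|---|---|---|
| 1.0 | 68% | 74% | 78% | 65% | 53% |
| 0.85 | 76% | 67% | 80% | 60% | 47% |
| 0.7 | 85% | 54% | 79% | 50% | 37% |
| 0.5 | 95% | 26% | 79% | 24% | 9% |

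The simulated loss for the score is 78 - 65 = 13 points at SD 1.0 and 79 - 24 = 55 points at SD 0.5. At SD 0.5 each outer class has about 130 × 0.0228 = 3 participants. In about two thirds of simulated trials an outer class had nobody in one arm, so its interaction could not be estimated; such runs count as non-significant in the last column.

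**Power for b = 3, n = 130.** The non-centrality is 130 × 9 / 1024 = 1.14, and continuous power is 19%. The score has 15% at SD 1.0 and 8% at SD 0.5. Over n = 110 to 130 the loss is about 3 to 10 points.

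**Step instead of trend.** With a 20-point step at the early cut, SD 1.0 and n = 130, the continuous term has about 38% power, the class score 48% and the three-class factor about 59%.

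**The case against.** The best defence is that the default is worded as a standard option, and Table 12 is a specific, pre-specified and referenced departure from it. That stands in part: pre-specification guards against choosing cuts after seeing results. It does not supply the missing reason.

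The second defence is about functional form. The only contrast that Table 12 names is late or average against early, which is a step at the early cut, and there the classes do better (about 59% against 38%). If only the average class differed from the other two, a linear term would miss it almost entirely: in a simulated case with an 18-point difference at SD 1.0, the factor had 74% power and the linear term 5%. This also stands, although the rationale concerns onset and not treatment response, and it would call for two classes, not three.

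Three stronger readings are tempting, and the documents do not support them.

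- A reader might infer a fixed loss of 13 to 55 points of power. That range needs an SD and a coding that the documents do not give, and an interaction of 8 points per SD, close to the whole 9-point target difference.
- A reader might infer that the cut removes most of the spread. At SD 0.7 to 1.0 a class score keeps 54% to 74% of the variance; only smaller SDs bear this out.
- A reader might infer from the single coefficient for timing that a class score will be used. The example output has 31 observations and "Residual standard error: 3105 on 28 degrees of freedom", so timing uses one degree of freedom. That rules out a three-level factor in the example but fits a continuous value equally well. A residual error of 3105 for a 0-100 scale also shows that the output is a placeholder.

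**Conclusion.** The point holds as a minor inconsistency with a cheap remedy: Table 12 departs, without a stated reason, from the plan's own default for a variable that the exception does not cover. Information is lost if moderation is graded. How much depends on the unknown SD of predicted age at peak height velocity, the size of the interaction and the coding. For a class score the loss is about 13 to 55 points of power at 8 points per SD and about 3 to 10 points at 3 points per SD. In the smaller case neither coding would be likely to detect moderation, so the change improves the analysis without rescuing it. This is not an error in the primary analysis: the unadjusted group comparison does not use growth timing, which reaches the primary model only if it is added as a covariate.

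**What to change.** In Table 12, make the main moderation and covariate term the predicted age at peak height velocity minus the sex-specific midpoint (11.94 for girls, 13.64 for boys), as a continuous value. For moderation, add its interaction with group. Centring by sex keeps timing from being mixed with sex. Keep the early, average and late classes for description or as a named sensitivity analysis, and state their coding there. Apply the same rule to the growth velocity offset, using the offset in years.

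The cost is a line or two in the SAP, dated before unblinding; both values must be computed anyway. The downside is the assumed linear trend and the lower power if the true effect is a step at the early cut, which is why the classes are worth keeping as a sensitivity analysis. If the classes are preferred as the main analysis, the plan should give the reason and state whether they enter as a factor or a score.

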Pressure sensitivity w4	Through handheld algometry, the patient denotes when pressure applied to the symptomatic tibial tubercle goes from feeling as "pressure" to "pain", and the kPa at this threshold is recorded. Change score is calculated from baseline.	The aim of the sports break is to calm the sensitivity of the condition to achieve a more successful graded exposure to sports and physical activity.  Besides pain intensity, one way to measure decreased sensitivity of the condition is through pressure-pain detection threshold to evaluate local hyperalgesia specifically at the tibial tubercle.					
Controlled return to sport w5	Sports participation in the preceding week is self- reported through weekly text messages, ranging from 0 to >7 hours. <2 hours of sports participation in week 5 will be considered as a controlled return to sport.	Graded exposure requires a gradual introduction to sports, although this trajectory quickly can be accelerated if it appears to be tolerated. In the very first week of a gradual return to sports, modest sports participation should be a marker of adhering to the recommendation of gradual return.					
Pain flare frequency during return to sport w13	Number of pain flares (episodes of NRPS ≥4) in the preceding week is self-reported through weekly text messages.	Graded exposure according to the pain-model aims to both prevent pain flares, and to mitigate their intensity to NRPS ≤3.					
Therapeutic Alliance w13	Therapeutic Alliance will be captured by participants filling in the 12 item short-form Working Alliance Inventory, each item scored on a 7-point likert scale with a score ranging from 0 to 84 points. 	Achieving a strong therapeutic alliance has been shown to be related to improved outcomes in trials across several musculoskeletal conditions. 					
Fear of movement w13	Fear of movement will be captured by participants filling in the 17 items Tampa Scale of Kinesiophobia, each item scored on a 4-point likert scale with a score ranging from 17 to 68. 	Avoidance behavior might be related to a too apprehensive approach to gradual exposure and exercise therapy resulting in the patient not achieving a higher degree of participation in sports and physical activity. Osgood-Schlatter patients exhibits a high degree of kinesiophobia. 					
Pain during maximal knee loading w13	Participants will rate their pain using NRPS 0-10 during strength testing, that is, a 5 second maximal voluntary isometric contraction of the knee extensor muscles at 60° knee flexion.	Pain during loading is a key symptom of Osgood-Schlatter and is related to self-reported measures of quality of life, satisfaction with sports participation and hyperemia in the tendon.  The intervention aims to improve capacity to loading activities and should thus be better tolerated at this timepoint.					
Knee extension strength w13	Knee extension strength will be measured in newtons by handheld dynamometry during a 5 second maximal voluntary isometric contraction at 60° knee flexion. Newtons will be normalized to lever-length and bodyweight and expressed as Nm/kg.	Knee pain is known to reduce muscle function,  and strength training contribute to alleviate these deficits. 					
Distal patella tendon hyperemia w13	Rated by sonographers ad modum Öhberg from 'no neovessels' to '5 or more neovessels' on a 1-4 scale. 	A series of Osgood-Schlatter patients has been described for whom less hyperemia on color doppler ultrasound was associated with milder symptoms.  Neovessels can generate and diminish rather quickly and could therefore be highly responsive to change in condition. 					
Infrapatellar bursitis sign w13	Either denoted as thickened bursa (yes/no) or appearing with doppler as rated by sonographers (1-4 nominal scale).	In our previous cohort at 2-year follow-up, almost all participar still experiencing knee-pain also had Flaviis grade 4 (associat infrapatellar bursitis) at baseline, whilst participants classified grade 1 (normal) were less likely to report pain at follow-up.  Thus, the sole finding of bursitis signs in the infrapatellar burs will be tested as mediator.					

Outcome					
Knee-related Function in Sport/Rec w22	Self-reported on KOOS-child 'Sport/play' subscale, which measure how painful certain movements related to sports- and recreational activities are perceived on 7 items ranging from 'no pain' to 'extreme pain' on a 1-5 Likert scale, normalized to a 0-100 score.	Primary outcome outcome collected at 22 weeks.			

### Statistical approach to mediation analysis

Mediation analysis will be based on interventional effects, this will allow for the inclusion of multiple mediators and account for dependence between mediators. With estimation done by Monte-Carlo based regressionmodels.Covariates will be included as moderators in the full model. For each mediator, we will calculate and report effect size as odds ratios and p-values, as well as 95% confidence intervals We will calculate and report estimated effect and percentage contribution to total effect for each mediator variable included in the final model, based of the mean indirect effect. The model will only include mediators that fulfill the temporal sequence of a causal relationship, that is exposure, mediator, outcome.

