## Statistical methods

## Statistical methods for primary and secondary outcomes (20a)

Analyses will be performed by a statistician blinded to group allocation and will be performed using (R Foundation for Statistical Computing, Vienna, Austria) in the Rstudio interface (RStudio Team, Boston, USA).

Change scores for KOOS-child 'sport/play' score ( $\triangle$ KOOS) from baseline to month 5 will be calculated for all participants. We will fit a linear regression model using the 'lm' function for  $\triangle$ KOOS-child as the dependent variable and including group allocation as an independent variable. Covariates are described with their measurement, timing and justification in table 12, and will potentially be added to the model.82(p9),215 In order to not introduce unnecessary bias in the model, covariates will however only be included if doing so changes the primary estimate meaningfully, as we expect a equal distribution of these pre-specified covariates given the sample size. Significance level will not determine the inclusion of covariates. The linear model will be evaluated for linearity, multicollinearity, homogeneity of variance, distortion of outliers, homoskedasticity, correlation of variables, distribution of residuals using histograms. If these model assumptions are not met non parametric bootstrap estimation and tests will be used instead. Below we have outlined the intended steps with reproducible R code for Rstudio (version 3.6, 2021.09.0+351)

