## Effect moderation and mediation

As secondary analyses, we will perform moderation and mediation (if a superior treatment response in arm A is observed) analyses, which will be conducted and reported in accordance with the AGReMA Statement. Through mediation analysis, the total effect of exposure to treatment groups 1 vs A (i.e. between-group difference) on the outcome, will be parsed into indirect effect pathways from exposure to mediator, and from mediator to the primary outcome (KOOS child 'Sport/play' subscale), which are the effects of interest in this mediation analysis (figure 4). This will allow inference about the underlying responsible mechanisms for a potential effect. Such knowledge is key when optimizing or developing treatments, and for implementation efforts. As the sample size is not planned specifically for mediation analysis, these analyses are considered secondary and should be interpreted with caution mainly based on its effect size and precision. Although potential limitations of suboptimal power, this mediation analysis provides a novel preliminary step for potential identification of causal mechanisms for improvement in Osgood-Schlatter patients.

Mediators are represented by variables measured after randomization and before collection of outcome data, which are thought or known to be influenced by the treatment allocated to participants. As large-scale randomization balances known and unknown confounders that can potentially influence the outcome as well as the exposure-mediator pathway, randomized trials are the optimal setting to perform causal mediation analysis.

The assumed cauasal model we are investigating is illustrated as a directed acyclic graph below (figure 5) using the Dagitty software.

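### Mediation effects are to be reported as odds ratios, which fit neither the numeric 0-100 KOOS-child outcome nor the decomposition planned in the next sentence

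*Combined protocol and SAP*

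**What the plan says.** Under *Statistical approach to mediation analysis* the framework is given first: "Mediation analysis will be based on interventional effects". The reporting rule follows: "For each mediator, we will calculate and report effect size as odds ratios and p-values, as well as 95% confidence intervals". The next sentence plans a second set of quantities, to be based on the mean indirect effect: "We will calculate and report estimated effect and percentage contribution to total effect for each mediator variable included in the final model".

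The outcome is fixed elsewhere. *Effect moderation and mediation* describes the second path as running "from mediator to the primary outcome (KOOS child 'Sport/play' subscale", and describes the total effect of treatment as the "i.e. between-group difference) on the outcome, will be parsed into indirect effect pathways". The outcome row of Table 12 places the score at week 22 and describes it as "normalized to a 0-100 score".

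For the same outcome in the primary analysis, *Statistical methods for primary and secondary outcomes* says: "We will fit a linear regression model using the 'lm' function". Logistic models appear later in that section with a limited use: "For non-numeric variables, differences between groups will be analyzed by logistic regression models".

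**The concern.** An odds ratio compares the odds of an event or of being in a higher ordered category. The mediation outcome, as specified, is a score in points and its total effect is a difference in points. Effects along the pathways of such a difference are also in points. The reporting sentence therefore asks for a measure that the specified outcome does not give.

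The effect size is the main thing a reader will take from this analysis. *Effect moderation and mediation* concedes that the trial was not sized for mediation and says the results should be judged mainly on effect size and precision. As written, the p-value and 95% confidence interval are tied to the odds ratio, while the percentage of the total effect is tied to the mean indirect effect. One mediator could then carry two results on different scales. An analyst who followed the odds-ratio sentence literally would have to choose a cut-point or an ordinal model that the plan does not contain.

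**Working it through.** The plan gives no figure on this point, so there is none to reproduce. The check compares the specifications and then uses a small illustration.

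**1. Outcome and model**

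| Element | What the plan specifies | Scale |
|---|---|---|
| Mediation outcome (Table 12, outcome row) | KOOS-child Sport/play, 7 items, 0-100, week 22 | points |
| Total effect (*Effect moderation and mediation*) | between-group difference on that outcome | points |
| Model for this outcome in the primary analysis | linear regression on change from baseline | points |
| Logistic regression | non-numeric variables only | odds ratio |
| Cut-point or ordinal model for Sport/play | none given | none |
| Mediator effect size, reporting sentence | odds ratio | odds ratio |
| Mediator effect size, next sentence | estimated effect and share of total, from the mean indirect effect | points and % |

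The reporting sentence is the only entry for the mediation outcome that is not in points or derived from points.

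**2. Could the odds ratio refer to the mediators themselves?** Table 12 lists ten:

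- Seven are numeric: worst pain, pressure threshold (kPa), number of pain flares, Working Alliance score, Tampa score, pain during maximal loading, and knee extension strength (Nm/kg).
- One is binary: controlled return to sport, under 2 hours in week 5.
- One is graded 1-4: tendon hyperemia.
- One is either yes/no or graded 1-4: bursitis sign.

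An odds ratio for the group-to-mediator path is conceivable for at most three of the ten. The reporting sentence covers every mediator, and that path is only the first half of an indirect effect. (*Number of predictors for mediations analysis* counts 8 mediators against the ten in Table 12. The argument does not depend on which count is right.)

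**3. Illustration of the scale problem.** Only the 9-point difference and the SD of 16 come from *Sample size considerations*. The other values are assumptions:

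- group effect on the mediator: -1.5 units, mediator SD 2
- mediator effect on the outcome: -2 points per unit
- direct effect: 6 points
- control mean change: 12 points

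In points:

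- Indirect effect = (-1.5) × (-2) = 3.0
- Total effect = 6 + 3.0 = 9
- Share = 3.0 / 9 = 33%

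The linear model gives these directly and gives no odds ratio. Exponentiating the indirect effect gives exp(3.0) ≈ 20, which is not the odds ratio of anything.

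If the change score is dichotomised, an odds ratio for the total effect can be formed as [p1/(1-p1)] / [p0/(1-p0)]. In a simulation of this model with 400,000 subjects:

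| Cut-point (points) | p1, arm A | p0, usual care | Odds ratio |
|---|---|---|---|
| 0 | 0.9057 | 0.7747 | 2.79 |
| 9 | 0.7745 | 0.5752 | 2.54 |
| 20 | 0.5271 | 0.3086 | 2.50 |
| 30 | 0.2858 | 0.1304 | 2.67 |
| 40 | 0.1168 | 0.0401 | 3.17 |

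The same 9-point effect gives odds ratios from about 2.5 to 3.2, depending only on a cut-point that the plan does not state.

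**The case against.** The best reply is that this is a slip of wording beside a usable measure. The sentence after it already plans an estimated effect and a percentage from the mean indirect effect, and a competent analyst would report those in points. The analysis is secondary, conditional on superiority, and flagged by the authors for cautious reading. All of this is correct and limits how far the point goes.

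Several stronger readings are tempting, and the documents do not support them:

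- **That no valid effect measure is planned.** One is, in the next sentence. The fault is a measure that does not fit and conflicts with it.
- **That the analyst is forced to dichotomise.** The mean indirect effect can be reported under the plan as it stands.
- **That the plan forbids dichotomising.** Keeping full resolution is its standard option. It allows collapsing of some assessor-rated categories, and Table 12 itself applies a cut to a mediator.
- **That dichotomising is the only route to an odds ratio.** A cumulative-logit model would give one for an ordered score without a cut-point. The plan names no such model for this outcome, so this does not rescue the sentence.
- **That effects in points must sum exactly, mediators plus direct effect, to the total.** With several dependent mediators, an interventional decomposition may contain a further term for that dependence. The one-mediator illustration has none.

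The mismatch itself survives these replies. None of them supplies a model in which an odds ratio for each mediator describes an effect on the specified outcome.

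**Conclusion.** The point holds as an incompatible and internally inconsistent effect measure. Odds ratios are specified for every mediator, the outcome and its total effect are in points, and the next sentence works from the mean indirect effect. The primary result, sample size and data collection are unaffected, and the analysis runs only if arm A is superior. It is still worth correcting, because effect size and precision are what the protocol asks readers to rely on here.

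The conclusion rests on one inference: the mediation section names Monte-Carlo based regression but no outcome model, so linearity is taken from the primary analysis and from the stated use of logistic regression. The odds ratios of 2.5 to 3.2 depend on assumed path values. They show only that the odds ratio varies with the cut-point.

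**What to change.** Replace the odds-ratio sentence with wording such as: *For each mediator, the interventional indirect effect will be reported as a mean difference in KOOS-child Sport/play points, with its p-value and 95% confidence interval.* Leave the following sentence in place and say that the percentage of the total effect is formed on the same scale. If the decomposition includes a term for dependence between mediators, show it separately.

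If odds ratios are truly wanted for the outcome, the plan must instead name the binary outcome with its cut-point and logistic model, or the ordinal model. Odds ratios for the group-to-mediator path of a binary or graded mediator can be shown, if labelled as such.

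No further rules are needed. The 95% intervals are already planned, so a particular interval method is a matter of preference. A condition on when to show percentages would add little, because mediation runs only after superiority is seen. The cost is one sentence in the SAP, with no change to sample size, data collection or the primary analysis.
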